**Lay Summary**

**BACKGROUND:** Phelan-McDermid syndrome (PMS) is a genetic form of autism spectrum disorder (ASD) associated with developmental delay and hypotonia. IGF-1 promotes brain vessel growth, neurogenesis, and synaptogenesis. Our previous clinical trial of IGF-1 in patients with Phelan McDermid Syndrome has shown improvement in core ASD symptoms using the Aberrant Behavior Checklist (ABC) and the Repetitive Behavior Scale-Revised (RBS-R). Growth hormone (GH) binds to its receptor and initiates a cascade of events which directly increases synthesis and release of IGF-1 levels.

**HYPOTHESIS:** We hypothesize that rise in IGF-1 stimulated by growth hormone (GH) administration should produce the same improvement in behavior in children and adolescents with Phelan McDermid Syndrome as previously demonstrated with use of IGF-1.

**RESEARCH PLAN:** We seek to recruit 20 patients with Phelan McDermid Syndrome and administer growth hormone as once daily subcutaneous injections for 12 weeks at standard doses. We will monitor baseline anthropometric measures, laboratory parameters for growth, IGF-1 levels, bone age prior to therapy and continue to monitor safety laboratory parameters during and after therapy. The goal of therapy would be to maintain IGF-1 levels between 1-2SD above the mean for age and puberty. Evaluations of their social withdrawal shall be made using standardized and validated behavioral scales. VEPs will be used as biomarkers of visual sensory reactivity. Each patient will have thorough history and physical evaluations prior to, during and following the trial.

**SIGNIFICANCE:** Autism is a severe lifelong neuro-developmental disorder. Our pilot trial of IGF-1 in patients with Phelan McDermid Syndrome demonstrated the improvement in their behavioral skills. Growth hormone is an easily accessible medication that has been studied for decades in children with short stature. Its safety profile is well known and administration in children is easier with once daily injections compared to twice daily injections with IGF-1. Also, hypoglycemia which is a serious adverse effect of IGF-1 therapy is not associated with growth hormone therapy. We expect growth hormone to produce similar effects to IGF-1 in these patients considering GH acts via the IGF-1 pathway. This project could perhaps make a breakthrough for treating children with all forms of autism in the future and must be explored.

**IF Number** IF2355548

## 2. Summary - Setup

Funding Has Been Requested / Obtained	Yes
Application Type	Request to Rely on Mount Sinai IRB
Research Involves	Prospective Study ONLY
Consenting Participants	Yes
Requesting Waiver or Alteration of Informed Consent for Any Procedures	No
Humanitarian Use Device (HUD) Used Exclusively in the Course of Medical Practice	No
Use of an Investigational Device to Evaluate Its Safety or Effectiveness	No
Banking Specimens for Future Research	No
Cancer Related Research that Requires Approval from the Protocol Review and Monitoring Committee (PRMC).	No

***Is this Cancer Related Research? Cancer Related Research is defined as research that has cancer endpoints or has a cancer population as part of or all of its targeted population. This includes protocols studying patients with cancer or those at risk for cancer.***

Clinical Trial	Yes
----------------	-----

\* A prospective biomedical or behavioral research study of human subjects that is designed to answer specific questions about biomedical or behavioral interventions (drugs, treatments, devices, or new ways of using known drugs, treatments, or devices).  
 \* Used to determine whether new biomedical or behavioral interventions are safe, efficacious, and effective.

Drugs / Biologics	Yes
-------------------	-----

\* Drugs / Biologics That Are Not a Part of Standard Practice  
 \* Controlled Substances  
 \* Drugs / Biologics Supplied by the Research Sponsor or Purchased with Study Funds

***Ionizing Radiation for imaging or therapy, including X-Ray, Fluoroscopy, CT, Nuclear Medicine, PET andor Radiation Therapy:***

* Purely for standard of care:	Yes
* In frequency or intensity that exceeds what is necessary for standard of care:	Yes

Hazardous Materials	No
---------------------	----

\* Recombinant DNA

- \* ***Viral Vectors***
- \* ***Plasmids***
- \* ***Bacterial Artificial Chromosomes***
- \* ***Toxic Chemicals, Potentially Toxic Medications, Carcinogens***
- \* ***Autologous Cell Lines***

**Request Use of Clinical Research      No**  
**Unit Resources**

### **3. Summary - Background**

#### **Objectives**

1. To evaluate if growth hormone will adequately elevate IGF-1 levels within 12 weeks of therapy.  
Hypothesis: Growth hormone will cause a rise in IGF-1 levels within 12 weeks of therapy.

2. To evaluate efficacy of growth hormone induced elevation in IGF1 on social withdrawal as the primary outcome measure using the ABC – Social Withdrawal subscale (Aman et al., 1985).

Hypothesis: Growth hormone will produce the same effects in improvement in social withdrawal as compared to IGF-1.

3. To evaluate efficacy of Growth hormone induced elevation in IGF1 on repetitive behaviors using the Repetitive Behavior Scale-Revised (Bodfish), sensory reactivity using the Short Sensory Profile (Dunn) and the Sensory Assessment for Neurodevelopmental Disorders (Siper et al., 2017), and hyperactivity using the ABC-Hyperactivity subscale.

Hypothesis: Growth hormone will be associated with improvement across all outcomes comparable with the use of IGF-1.

4. To evaluate the effect of growth hormone therapy on visual evoked potentials and auditory event related potentials in children with Phelan McDermid Syndrome.

Hypothesis: Growth hormone will be associated with similar changes in visual evoked potentials and auditory event related potentials following 12 weeks trial as compared to IGF-1.

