Growth hormone binds to its receptor and initiates a cascade of events which involves transcription of several genes resulting in rise of IGF-1. (Vottero et al., 2013, Hormone Resistance and Hypersensitivity; Ashpole et al., 2015, Experimental Gerontology). We hypothesize that increase in IGF-1 stimulated by growth hormone administration should produce the same improvement in behavior in children and adolescents with Phelan McDermid Syndrome as previously demonstrated with use of IGF-1 ([name] et al., 2014).

Growth hormone is an easily available drug whose safety profile has been studied since 1985 (Ranke et al.; 2018). The experience with growth hormone has shown that it is well tolerated by children with few adverse effects as compared to IGF-1. Hypoglycemia is not associated with growth hormone therapy while it is a serious adverse event with IGF-1 therapy, requiring serial monitoring. Growth hormone is also easy to administer as a once daily subcutaneous dose compared to the twice daily subcutaneous injections for IGF-1.

Hence, administration of growth hormone may be a viable option to increase IGF-1 levels and have an impact on the behavior of these children.

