#### **Primary and Secondary Study Endpoints**

1. Improvement in social withdrawal following growth hormone administration measured using the ABC - Social Withdrawal Subscale and repetitive behavior using the Repetitive Behavior Scale-Revised.
2. Improvement in other behavioral scales following growth hormone administration, such as the Short Sensory Profile, Sensory Assessment for Neurodevelopmental Disorders, and the ABC-Hyperactivity subscale as seen with the IGF-1 trial.
2. VEPs will show improvement in amplitudes in children with Phelan McDermid Syndrome following 12 weeks of growth hormone therapy, similar to the changes seen following IGF-1 therapy.

---

**Protocol Was Already Approved** No  

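### Hypotheses 2 to 4, the overall hypothesis and the VEP endpoint claim effects the same as or similar to IGF-1, but no planned analysis compares GH with IGF-1

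*Combined protocol and SAP*

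**What the plan says.** Section 3, Objectives, gives each objective a hypothesis.

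- Hypothesis 2, on ABC-Social Withdrawal as the primary outcome measure: "Growth hormone will produce the same effects in improvement in social withdrawal as compared to IGF-1".
- Hypothesis 3, on repetitive behaviour, sensory reactivity and hyperactivity: "Growth hormone will be associated with improvement across all outcomes comparable with the use of IGF-1".
- Hypothesis 4, on electrophysiology: "Growth hormone will be associated with similar changes in visual evoked potentials and auditory event related potentials", again relative to IGF-1.

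The overall hypothesis says the same. In the Lay Summary, the GH-driven rise in IGF-1 "should produce the same improvement in behavior in children and adolescents with Phelan McDermid Syndrome as previously demonstrated with use of IGF-1". In section 3, Background, the "increase in IGF-1 stimulated by growth hormone administration should produce the same improvement in behavior". Under Primary and Secondary Study Endpoints, the VEP item begins "VEPs will show improvement in amplitudes in children with Phelan McDermid Syndrome" and ends "similar to the changes seen following IGF-1 therapy".

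The design is one group on GH for 12 weeks without placebo (section 12, Drug Administration; repeated in section 22, Selection Procedures to Minimize Toxicity). Section 21, Power Analysis/Data Analysis Plan, lists three analyses: change scores between baseline and week 12, a GLMM with VEP as a time-varying covariate, and a correlation between VEP change and clinical change. All tests are two-sided at .05.

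**The concern.** A claim that one treatment works as well as another needs three things: data or a reference value for the other treatment, a definition of how close is close enough, and a method that compares the two. The analysis plan has none of these.

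What is at stake is the conclusion. If ABC-Social Withdrawal improves significantly on GH, a reader who holds that result against hypothesis 2 as worded will be inclined to conclude that GH matches IGF-1. The same result would fit a GH effect well below that of IGF-1. Rewording after the data are in would look driven by the result, so the change belongs before analysis.

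**Working it through.** **Step 1. Claims against analyses.**

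| Statement | What it needs | What is planned |
|---|---|---|
| Hypothesis 2 (same effects, social withdrawal) | GH against IGF-1 | Change within the GH group |
| Hypothesis 3 (comparable, other scales) | GH against IGF-1 | Change within the GH group |
| Hypothesis 4 and the VEP endpoint (similar changes) | GH against IGF-1 | Change, VEP-covariate GLMM and correlation, all within the GH group |
| Objectives 2 to 4 and the first endpoint | Change on GH | Change within the GH group: matches |

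Hypothesis 1, a rise in IGF-1 on GH, is a within-group claim and is not affected.

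**Step 2. The plan's own power figure.** Sections 7 and 21 state 80% power at .05 for effects described only as moderate to large, and name a treatment-by-time interaction. No numerical effect size is given, so the figure cannot be strictly reproduced. A one-sample t-test of change with 20 patients reaches 80% power at a true change of 0.66 SD. The description therefore fits a test of change against zero, though in words only. The interaction names no second group, so it does not supply a comparison with IGF-1.

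**Step 3. What a significant change shows.** Inputs: n = 20 (section 6) and two-sided .05 (section 21). The paired t-test is assumed, and effects are in SDs of the change score because no SD is given.

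- Critical value: t(19, .975) = 2.093.
- Smallest significant observed change: 2.093 / √20 = 0.468 SD.
- 95% CI at that point: 0.468 ± 0.468, that is 0 to 0.936 SD.

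The threshold is the same whatever IGF-1 achieved.

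**Step 4. A GH effect half as large as that of IGF-1.** The IGF-1 effects are assumptions. Power comes from the noncentral t distribution with 19 df and noncentrality d√20.

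| Assumed IGF-1 effect | GH effect d (half) | d√20 | Probability of a significant improvement |
|---|---|---|---|
| 0.8 SD | 0.4 SD | 1.79 | 0.397 |
| 1.0 SD | 0.5 SD | 2.24 | 0.564 |
| 1.2 SD | 0.6 SD | 2.68 | 0.721 |

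In these scenarios sameness is false by construction, yet 40% to 72% of trials would give a significant result.

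**The case against.** The strongest reply is that the operative parts of the protocol are not comparative. Objectives 2 and 3 are to evaluate efficacy, objective 4 is to evaluate an effect of GH, and the first endpoint is improvement after GH. The study is a pilot, and no section says that a significant change will be reported as sameness. This stands in part: it limits the problem to the hypothesis sentences and one endpoint clause. It does not remove it, because those sentences are labelled as hypotheses and one belongs to the primary outcome measure.

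It can also be said that the same effects means only effects in the same domains. That reading is fair for the second endpoint item, where "as seen with the IGF-1 trial" may refer only to the choice of scales, so that item is not counted here. It does not fit hypothesis 2, which makes an explicit comparison with IGF-1, or the overall hypothesis, which speaks of the same improvement.

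A fuller analysis plan may exist. The GLMM is called additional, which implies a base model that is not described, and section 27 lists a separate Research Plan file. The point is therefore limited to the text supplied. If a comparison is specified elsewhere, section 21 still needs to agree with it.

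Finally, Steps 3 and 4 rest on an assumed test and assumed effects. That is so; they illustrate the size of the gap, and the gap itself does not depend on them.

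**Conclusion.** The sameness claims in hypotheses 2 to 4, the overall hypothesis and the VEP endpoint cannot be supported by any analysis in the text supplied. With 20 patients, a paired t-test and two-sided .05, a just-significant result is compatible with anything from no change to 0.94 SD. A GH effect half that of IGF-1 would be significant in 40% to 72% of trials if the IGF-1 effect were 0.8 to 1.2 SD. The documents state neither the SD nor the IGF-1 effect.

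Three stronger conclusions that a reader might draw are not supported:

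- That the trial cannot answer its objectives. It can, because they ask about change on GH.
- That change from baseline is the only analysis. The GLMM and the correlation are also planned, but neither involves IGF-1.
- That the trial needs a formal comparison with the earlier IGF-1 patients. The plan proposes none, and the mismatch can be removed without one.

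**What to change.** Amend the wording before any outcome data are analysed.

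1. Hypothesis 2: *ABC-Social Withdrawal will improve from baseline to week 12 of GH.*
2. Hypothesis 3: *RBS-R, Short Sensory Profile, SAND and ABC-Hyperactivity will improve from baseline to week 12 of GH.*
3. Hypothesis 4: *VEP amplitudes will improve, and auditory event related potentials will change, from baseline to week 12 of GH.* The direction for VEP is the one already in the endpoint; none is stated for the auditory measure.
4. In the VEP endpoint, delete "similar to the changes seen following IGF-1 therapy".
5. Align the overall hypothesis in the Lay Summary and in section 3, Background. In the Significance paragraph of the Lay Summary, present the expectation that GH will act much like IGF-1 as rationale only.
6. Add to section 21: *A change from baseline in the GH group will not be reported as sameness with IGF-1.*

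This needs no new patients, visits or analyses, and the IGF-1 pathway argument can stay as background. The cost is an amendment and a less favourable conclusion: the trial may report a change on GH, but not that GH does what IGF-1 did.

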#### **Background**

In recent years there have been major changes in the understanding of the etiology of autism spectrum disorders (ASD) and many genes associated with ASD have been identified. This has led to a profound shift in thinking, such that ASD can now be conceived of as having multiple independent causes, which in many cases can be largely attributed to a specific etiological genetic event. One such example is the 22q13 deletion syndrome, also called Phelan-McDermid syndrome (PMS), characterized by global developmental delay, hypotonia, delayed or absent speech, and ASD features, for which convincing evidence implicates SHANK3 as the critical gene (Bonaglia et al, 2006). SHANK3 codes for a master scaffolding protein which forms the framework in glutamatergic synapses (Boeckers et al, 2006) and makes up the core of the postsynaptic density (PSD). Recent studies exploring the rate of 22q13 deletions/SHANK3 mutations suggest that haploinsufficiency of SHANK3 can cause a monogenic form of ASD and intellectual disability with a frequency of up to 2% of ASD cases (Durand et al, 2007; Moessner et al, 2007; Gauthier et al, 2008; LeBlond et al., 2015). Although SHANK3 mutations and deletions account for a relatively small proportion of ASD cases, recent evidence suggests that this variant may be treatable, and therefore important to identify.

Work on PMS at our Center began with Shank3-deficient mice showing a reduction in basal neurotransmission reflecting decreased glutamate (i.e., AMPA receptor-mediated) transmission. Long-term potentiation was impaired with no significant change in long-term depression (Bozdagi et al., 2010), and intraperitoneal injection of IGF-1 reversed the electrophysiological and motor deficits seen in the Shank3-deficient mice (Bozdagi et al., 2013).

Our clinical group began prospectively evaluating patients with PMS using standard evaluation tools in 2010; 65 affected individuals have been seen to date at our site and an additional 54 participants have been evaluated across our national PMS network and will be leveraged to meet recruitment goals for this project. We have published descriptive results from 32 patients thus far, 27 of whom (84%) met criteria for ASD using a priori definitions derived from expert consensus commonly used in ASD research (Soorya et al., 2013). Subsequently, we began a controlled trial of IGF-1 in PMS and provided evidence of improvement in core ASD symptoms ([name] et al., 2014) using the Aberrant Behavior Checklist (ABC; Aman et al., 1985) and the Repetitive Behavior Scale-Revised (RBS-R; Bodfish et al., 2000). IGF-1 also reversed phenotypic and electrophysiological changes in human neuronal models of PMS (Shcheglovitov et al., 2013) and iASD (Marchetto et al., 2016), providing additional support for this intervention.

IGF-1 enters the brain from the circulation where it is released mainly by the liver upon growth hormone stimulation. Blood-borne IGF-1 is found in the CNS and promotes brain vessel growth (Lopez-Lopez et al., 2004), neurogenesis, and synaptogenesis (O'Kusky et al., 2000). Once IGF-1 binds to the IGF-1 receptor, activation of the PI3K/mTOR/ AKT1 and MAPK/ERK pathways induces its downstream effects (Costales & [name], 2016). A recent study in Rett syndrome provides evidence of IGF-1 brain penetrance: cerebrospinal fluid and serum analysis revealed significant increases in IGF-1 levels after treatment (Khwaja et al., 2014).

The proposed clinical trial seeks to collect pilot data on the role of exogenous growth hormone in children and adolescents with Phelan McDermid Syndrome to increase IGF-1 levels, which has been shown to have positive effects on social withdrawal, repetitive behaviors, sensory reactivity, and hyperactivity. There is currently no treatment available for PMS and the use of growth hormone may be practical and effective.

Growth hormone binds to its receptor and initiates a cascade of events which involves transcription of several genes resulting in rise of IGF-1. (Vottero et al., 2013, Hormone Resistance and Hypersensitivity; Ashpole et al., 2015, Experimental Gerontology). We hypothesize that increase in IGF-1 stimulated by growth hormone administration should produce the same improvement in behavior in children and adolescents with Phelan McDermid Syndrome as previously demonstrated with use of IGF-1 ([name] et al., 2014).

Growth hormone is an easily available drug whose safety profile has been studied since 1985 (Ranke et al.; 2018). The experience with growth hormone has shown that it is well tolerated by children with few adverse effects as compared to IGF-1. Hypoglycemia is not associated with growth hormone therapy while it is a serious adverse event with IGF-1 therapy, requiring serial monitoring. Growth hormone is also easy to administer as a once daily subcutaneous dose compared to the twice daily subcutaneous injections for IGF-1.

Hence, administration of growth hormone may be a viable option to increase IGF-1 levels and have an impact on the behavior of these children.

#### **Primary and Secondary Study Endpoints**

1. Improvement in social withdrawal following growth hormone administration measured using the ABC - Social Withdrawal Subscale and repetitive behavior using the Repetitive Behavior Scale-Revised.
2. Improvement in other behavioral scales following growth hormone administration, such as the Short Sensory Profile, Sensory Assessment for Neurodevelopmental Disorders, and the ABC-Hyperactivity subscale as seen with the IGF-1 trial.
2. VEPs will show improvement in amplitudes in children with Phelan McDermid Syndrome following 12 weeks of growth hormone therapy, similar to the changes seen following IGF-1 therapy.

---

**Protocol Was Already Approved** No  

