**To Complete Study**

**Feasibility of Meeting Recruitment Goals**

Power is calculated for differences in baseline to week 12 change scores. Testing for treatment x time interactions and # at .05, we have 80% power to detect moderate to large effects.

Based on data from our previous clinical trial of IGF-1 in patients with Phelan McDermid Syndrome, a 12 week study was feasible in 9 patients.

We feel that 20 patients would provide adequate data to establish the utility of growth hormone in this population. The Seaver Autism Center has access to this population of children with Phelan McDermid Syndrome which should help facilitate recruitment.

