### **Power Analysis/Data Analysis Plan (Including Any Statistical Procedures)**

The model for this design is baseline to week 12 change scores. To examine whether electrophysiological markers track changes in clinical profiles, we will fit an additional GLMM with VEP values included as a time-varying rather than baseline covariate. If treatment effects become less significant it will suggest that GH is acting on clinical outcomes through the biomarker. Finally, we will directly correlate week-12 change scores for VEP and clinical measures. All tests will use a two-sided # of .05.

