### **Power Analysis**

Power is calculated for differences in baseline to week 12 change scores. Testing for treatment x time interactions and # at .05, we have 80% power to detect moderate to large effects.

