**Contact**

**Funding Category** Foundation

**Meditrack (<https://contracts.tractmanager.com/Contracts/Login.aspx>)** [Meditrack \(<https://contracts.tractmanager.com/Contracts/Login.aspx>\)](https://contracts.tractmanager.com/Contracts/Login.aspx)

**Grant or Contract Title** An Open Label Trial of Growth Hormone in Children and Adolescents with Phelan-McDermid Syndrome Targeting Social Withdrawal and Repetitive Behavior

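### Objective 2 makes ABC-Social Withdrawal the primary outcome, but the endpoint list joins it with RBS-R in an unlabelled first item, so an RBS-R result could be reported as the main finding

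*Combined protocol and SAP*

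**What the plan says.** Section 3, *Objectives*: Objective 2 evaluates growth hormone "on social withdrawal as the primary outcome measure using the ABC" Social Withdrawal subscale. RBS-R appears in Objective 3, beside the Short Sensory Profile, the Sensory Assessment for Neurodevelopmental Disorders and ABC-Hyperactivity.

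Section 3, *Primary and Secondary Study Endpoints*: item 1 is improvement in social withdrawal "measured using the ABC - Social Withdrawal Subscale and repetitive behavior using the Repetitive Behavior Scale-Revised". The next item begins "Improvement in other behavioral scales following growth hormone administration" and covers the two sensory instruments and ABC-Hyperactivity. A third item, also numbered 2, covers visual evoked potentials (VEPs). The heading promises two tiers, but no item carries either label.

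Sections 7 and 21, power: "Power is calculated for differences in baseline to week 12 change scores" and "Testing for treatment x time interactions and # at .05, we have 80% power to detect moderate to large effects". Neither section names a scale.

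Section 21, data analysis plan: the model is change from baseline to week 12, followed by an additional mixed model with VEP and by correlations of VEP change with clinical change. It ends: "All tests will use a two-sided # of .05". (The # marks a symbol lost in text conversion.) It names no primary scale and does not say which test carries the main conclusion.

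Two other places pair the domains. The grant title in section 23 ends "Targeting Social Withdrawal and Repetitive Behavior", and the IND-exemption justification in section 25 describes the pilot as looking at both.

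**The concern.** The endpoint section is where a reader looks to learn what the trial's main conclusion rests on, and it groups the scales differently from the objectives. The objectives put RBS-R with the sensory and hyperactivity scales. The endpoint list puts it with ABC-Social Withdrawal and calls everything after that other. A reader who takes the order of the list as tiers arrives at a two-part primary.

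This matters when the scales disagree. If RBS-R improves and ABC-Social Withdrawal is not significant, Objective 2 says the primary outcome was not met, while item 1 gives cover for presenting RBS-R as the main result. The trial is open-label with one group (section 12), and both scales are parent-rated. Naming one endpoint in advance is among the few protections it has against selective emphasis.

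**Working it through.** **1. The texts side by side**

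| Place | ABC-Social Withdrawal | RBS-R | Labelled primary? |
|---|---|---|---|
| Section 3, Objectives | Objective 2 | Objective 3, with other scales | Yes, ABC-Social Withdrawal only |
| Section 3, endpoint list | Item 1 | Item 1 | No item labelled |
| Sections 7 and 21, power | Not named | Not named | No |
| Section 21, analysis plan | Not named | Not named | No |
| Sections 23 and 25 | Domain paired with repetitive behavior | Domain paired with social withdrawal | No |

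Objective 2 is the only text that names a primary.

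**2. The plan's own figure.** The 80% power cannot be strictly reproduced, because no effect size, standard deviation or scale is given. For a one-sample t-test on change scores with n = 20 (19 degrees of freedom, critical value 2.093),

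power(d) = P(|T| > 2.093), where T is noncentral t with noncentrality d√20.

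This gives 0.565 at d = 0.5, 0.800 at d = 0.66 and 0.924 at d = 0.8. The claim of 80% power for moderate to large effects is therefore compatible with one scale and d of about 0.66. The treatment-by-time wording does not fit a single-group design and is not used here.

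**3. How often RBS-R improves while ABC-Social Withdrawal is not significant.** Assumptions, none of them stated in the documents: 20 completers, a one-sample t-test on each scale at two-sided .05, bivariate normal changes, the same d on both scales, and correlation ρ of 0, 0.5 or 0.9.

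At ρ = 0 the probability is power × (1 − power):
- d = 0.5: 0.565 × 0.435 = 0.246
- d = 0.66: 0.800 × 0.200 = 0.160

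For ρ > 0, simulation with 400,000 trials per cell gives:

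| d | ρ = 0 | ρ = 0.5 | ρ = 0.9 |
|---|---|---|---|
| 0.5 | 24.6% | 16.9% | 7.4% |
| 0.66 | 16.0% | 11.6% | 5.3% |

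Check: with equal d the same quantity is power minus P(both significant). At d = 0.5 and ρ = 0.5, 0.565 − 0.397 = 0.168. At d = 0.66 and ρ = 0.9, 0.800 − 0.747 = 0.053. Both agree with the table to within 0.1 percentage point.

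**4. No true change on either scale.** One scale shows false improvement with probability 0.025. For at least one of two:
- ρ = 0: 1 − 0.975² = 0.0494
- ρ = 0.5: 0.0457 (simulated)
- ρ = 0.9: 0.0360 (simulated)

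These rates assume zero average change without the drug, which a single-group design cannot guarantee.

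**The case against.** The strongest reply is that Objective 2 already answers the question. It names ABC-Social Withdrawal, nothing calls RBS-R primary, and the endpoint heading covers both tiers, so the list can be read consistently with the objectives as loose drafting. The repeated item number may be a typing slip. The grant title and exemption text describe a topic and do not define endpoints. Much of this stands. A reader might infer that the protocol declares two competing primaries, or that it intends a both-or-either success rule. The documents support neither: RBS-R is never called primary and no such rule appears. What remains is that the endpoint section regroups the scales without labels and the analysis plan does not settle the matter.

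A reader might also lean on other sections, such as the Lay Summary and the expected benefit in section 10, as stressing social withdrawal alone. Their sentences about this trial's target do, but both also cite the earlier IGF-1 trial's RBS-R results. They do not decide the point.

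A third reply is that this is a small open pilot, not aimed at a new indication, in which even a significant primary would not isolate a drug effect. That is correct and limits the weight of the point. It does not remove it, because the plan states hypotheses, claims 80% power and expects 20 patients to show whether growth hormone is useful in this population.

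**Conclusion.** The point holds as an inconsistency between the objectives and the endpoint list that leaves room for selective reporting. It deserves correction before outcome data are seen, and it does not undermine the design.

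Under the assumptions shown, the pattern that matters arises in about 25% / 17% / 7% of trials at d = 0.5 and 16% / 12% / 5% at d = 0.66, for correlations 0 / 0.5 / 0.9. It is less common when the scales move closely together or the effect is larger.

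Two larger numbers are tempting and should not be used:
- The chance that exactly one scale is significant (49% / 34% / 15% at d = 0.5) is about twice the relevant figure. Half of it is ABC-Social Withdrawal succeeding alone, which Objective 2 already treats as success.
- The two-sided chance of at least one false positive (1 − 0.95² = 9.75% at zero correlation) counts worsening as well. False improvement is at most about 4.9%, against 2.5% for one scale. That is up to a doubling, but from a low base.

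The effect sizes, correlations, equal effects and full follow-up are assumptions. The Research Plan listed in section 27 was not available and may label the endpoints.

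**What to change.** In section 3, *Primary and Secondary Study Endpoints*, label change from baseline to week 12 in ABC-Social Withdrawal as the single primary endpoint, matching Objective 2. List RBS-R, the other behavioral scales and VEP as secondary. State which RBS-R score is meant; section 12 supports either the total or the subscales, so that choice is the sponsor's.

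In section 21, state that the main conclusion rests on the baseline to week 12 change in ABC-Social Withdrawal at two-sided .05, and that all other tests are kept and reported as secondary or exploratory. This covers the VEP mixed model and the VEP-clinical correlations. It also gives a status to tests of IGF-1 levels and auditory event related potentials, which are objectives but are missing from the endpoint list.

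The cost is wording in two sections. No subjects, visits or data are added and no test is dropped. The downside is that an RBS-R improvement alone could not be claimed as meeting the primary, although the grant title and section 25 pair the two domains. On the assumptions above, the sponsor gives up that claim in the share of trials shown in step 3 of the working. The relabelling does not supply a comparator, so a significant primary would still not separate a drug effect from time or expectancy.
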